5.7 Criteria for Removal from Study Treatment

Subjects may be removed from study treatment for any of the following:

- Intercurrent illness that prevents further administration of treatment,
- Patient's decision to withdraw from the study treatment,
- Deterioration in the patient's condition rendering the patient unacceptable for further treatment in the judgment of the investigator. This may include, but is not limited to, progression in comorbid diseases that become more life threatening, deterioration of performance status unrelated to the trial, or any other situation in which continuation of treatment on this study would be detrimental to the health of the patient at the discretion of the treating physician.

Early Study Treatment Discontinuation or Study Termination

In accordance with good medical practice, any ongoing study drug-related adverse event present at study termination, including a clinically significant laboratory test abnormality, will be followed until resolved or until the event stabilizes and the overall clinical outcome has been ascertained. Skin photographs will be continued for adverse events which take place in the radiation field until resolution. Adverse events starting up to 30 days after the last dose of study medication may be collected by telephone contact.

Page 11 of 23

6 TREATMENT EVALUATION

6.1 Calendar of Study Assessments & Testing

		Head/Neck RT(Weekly) ^a								
	Baseline	Week 1	Week 2	Week 3	Week 4	Week 5	Week 6	Week 7	Week 8	Week 9 ^h
SCREENING										
Written Informed Consent	Х									
Inclusion/Exclusion Criteria	Х									
PHYSICAL										
Comprehensive History and Physical (ECOG only at Baseline)	Х									
Focused Skin Exam (Radiation Oncologist)	Х	Х	Х	Х	Х	Х	Х	Х		
Medical Photography ^d	Χ	X	Х	Х	Х	Х	Х	Х		
ASSESSMENTS										
CTCAE Version 5 Radiation Dermatitis (Radiation Oncologist)		Х	Х	Х	Х	Х	Х	Х		
CTCAE Version 5 Radiation Dermatitis (Blinded – Dermatologist)		Х	Х	Х	Х	Х	Х	Х		
Adverse Events/Toxicity		Х	Х	Х	Х	Х	Х	Х		
SkinDex16 Questionnaire	Χ	Х	Х	Х	Х	Х	Х	Х		
TREATMENT										
CT Simulation	Х							Χg		
XRT		Х	Х	Х	Х	Х	Х	Х		
Dermaprazole or Aquaphor ^c	Х	Х	Х	Х	Х	Х	Х	Х	Х	Х
Compliance Assessment	X ^f	X	Х	Х	Х	Х	Х	Х		Х
LAB DRAW										
Serum Pregnancy Test if Woman of Child-Bearing Potential	Х									
WBC, Hgb, ALT, AST, creatinine, calcium captured from clinical labse	Х	Х	Х	Х	Х	Х	Х	Х	Х	Х
Research Blood Draw to Central Lab: CRP, TNFa, IL-1b, IL-6	X							Xp		Х

- (a) Weekly assessments to be performed within +/- 3 days of the end of each week (defined by a period of 5 treatments).
- (b) In the last week of radiotherapy, may be different than week 7 $\,$
- (c) See Section 5.3 for detailed instructions regarding Dermaprazole and Aquaphor
- (d) Photos will be taken with a Canon EOS Rebel T7 DSLR Camera with 18-55mm Lens. Photos will be uploaded to a protected research folder directly from the camera and the dermatologist will have access to the folder. The photos will be de-identified and labeled with study case number.
- (e) WBC, Hgb, ALT, AST, creatinine and calcium data will be obtained from standard care clinical labs during treatment. If labs are not being drawn then they will not be obtained for the study.
- (f) Compliance assessment may be performed by telephone by research staff from Baseline to start of XRT
- (g) CT Simulation to be done anytime during the last 7 days of radiation treatment
- (h) Week 9 is defined as 2 weeks post last radiation treatment ± 5 day

Page 12 of 23

	Post-Treatment Assessment		Long Term Follow-Up Up to 60 months post-tx		
	Month 1 30 days post-tx ⁱ	Month 3 90 days post- ^{txj}	Every 3 Months M6, M9, M12j	Every year M24, M36, M48, ^{M60j}	
PHYSICAL					
Focused Skin Exam (Radiation Oncologist)	X	X	X	X	
Medical Photography	X	X	X	X	
ASSESSMENTS					
CTCAE Version 5 Radiation Dermatitis (Radiation Oncologist)	Х	Х	Х	Х	
CTCAE Version 5 Radiation Dermatitis (Blinded – Dermatologist)	X	X	Х	X	
Adverse Events/Toxicity	X ^k	X ^k	X ^k	X ^k	
SkinDex16	Х	Х	Х	X	

Note: Timing of post-treatment visits is from the completion of radiotherapy

- (i) To be completed within +/- 14 days
- (j) To be completed within +/- 28 days
- (k) See Section 10.5.

6.2 Treatment Evaluation

A general history and physical must be done within 12 weeks prior to registration. Pathologic diagnosis of the tumor must be done within 6 months prior to registration.

After completion of chemoradiation, patients will be seen at one, three, six, nine, and twelve months for an adverse events/toxicity check and clinical evaluation of skin by a radiation oncologist during the first year. Subsequent evaluation at two, three, four and five years will be completed to assess for long-term adverse events/toxicities. Medical photographs will be obtained for review by a board-certified dermatologist. See study calendar.

7 MEASUREMENT OF EFFECT

Rates and severity of radiation-related toxicity will be defined using NCI Common Terminology Criteria for Adverse Events version 5. These will be used in assessment by the treating radiation oncologist as well as during blinded review by the dermatologist.

The following definitions will be used:

• Grade 1: Mild; asymptomatic or mild symptoms; clinical or diagnostic observations only; intervention not indicated

Page 13 of 23

- o Faint erythema or dry desquamation
- Grade 2: Moderate; minimal, local or noninvasive intervention indicated; limiting ageappropriate instrumental activities of daily living (ADL)
 - o Moderate to brisk erythema; patchy moist desquamation, mostly confined to skin folds and creases; moderate edema
- Grade 3: Severe or medically significant but not immediately life-threatening; hospitalization or prolongation of hospitalization indicated; disabling; limiting self-care ADL
 - Moist desquamation in areas other than skin folds and creases; bleeding induced by minor trauma or abrasion
- Grade 4: Life-threatening consequences; urgent intervention indicated.
 - O Skin necrosis or ulceration of full thickness dermis; spontaneous bleeding from involved site; skin graft indicated
- Grade 5: Death related to adverse event.

Compliance to intervention and use of other topical agents will be documented qualitatively during weekly assessments. Patient's effect on quality of life will be evaluated using SkinDex 16 (Appendix 1).

8 STATISTICAL CONSIDERATIONS

8.1. Study Design/Endpoints

This portion of the study is designed to evaluate toxicity profile and preliminary efficacy of prophylactic Dermaprazole cream for radiation dermatitis in head and neck cancer patients receiving chemoradiation.

The first primary outcome is rates of clinically significant radiation dermatitis as defined as NCI CTCAE version 5 grade 2 or higher. Although not expected, if half our expected enrollment in the Dermaprazole group, 50% or more of patients experience moderate intervention-related toxicity, this treatment regimen will not be considered safe. The trial will be monitored for SAEs and stopped early for safety if two treatment-related grade 3 SAEs are reported or if one treatment-related grade 4-5 SAE is reported at any point of the trial for the Dermaprazole group.

Another primary endpoint will be feasibility, which is defined as the consideration of whether the protocol implementation will be successful in terms of accrual within the expected timeframe, as well as whether patients would comply with the study protocol and necessary data collection is logistically feasible in the clinical setting. To evaluate feasibility, we will measure:

Page 14 of 23

- Accrual rate and summary of causes for non-enrollment
- Percentage of patients compliant with therapy, defined as receiving at least 60Gy to the head and neck while using prophylactic Dermaprazole as directed
- Compliance rate and rate of completion of SkinDex16 forms

All endpoints will be evaluated when the last patient completes their 3 Month follow-up visit, although patients will continue with additional regular follow-up visits as described in the protocol schedule. Since by that point a patient would have completed all treatments, the data would provide accurate estimate of compliance and acute toxicity.

For the study to be considered feasible, all of the following must be true:

- No more than 5 patients fail to complete the treatment regimen due to study drug toxicity
- No more than 15 patients fail to comply to prophylactic Dermaprazole cream application of at least 80%
- Enrollment takes no longer than 24 months, and
- Proportions of analyzable questionnaires at baseline, while on-treatment, and offtreatment during follow-up, and within questionnaires completion rates are no worse than 80%, 80%, and 60% respectively.

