8.2 Sample Size/Accrual Rate

Participants will continue to be enrolled and monitored for toxicity per the above criteria until 30 patients in arm 1 and 15 patients in arm 2 have completed the course of head and neck radiation as evaluable patients. Patients will be randomized by computer in a 2:1 fashion. Per our current database, the clinic is treating approximately 60 eligible patients per year. As such, accrual should take no longer than 12 months but will be allowed to extend to up to 24 months without closing the study.

Initial sample size for this pilot study was estimated as if this study was conducted as a phase II study. Sample size calculation was determined using significance/alpha (α) of 0.05, to at least detect a difference in incidence of 45% and power (β) of 80%. In general, rates of clinically bothersome grade II dermatitis in the literature appear to be approximately 65%. Based on our preclinical study with animal and human skin models, we expect 20% of the Dermaprazole arm to have CTCAE grade II or higher RD. Given these values, we calculated our final sample size to be approximately 39 and we aim to enroll 45 subjects.

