8.4 Reporting and Exclusions

All patients enrolled in this study who complete at least 60Gy of radiation and follow up at 30 days post treatment will be included in the analysis.

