10.4 Management of Adverse Events and impact on treatment

- Expected mild/moderate toxicity (Grade 1-2) will be managed conservatively by the treating physician.
- Unexpected or severe adverse events will be managed on a case by case basis at the discretion of the treating physician in coordination with the study team. Emergent dermatology consult and face-to-face evaluation within 48 hours will be sought for each suspected intervention-related adverse effect. Every effort will be made to continue radiation treatments for the prescribed duration, as would be the standard of care. If the risks of continuation of any portion of the patients' treatment is felt to immediately outweigh the benefits or be detrimental to the patient, it may be temporarily withheld at the discretion of the treatment team.
- Adverse events directly related to Dermaprazole may prompt withdrawal from the study. Radiation will continue as scheduled unless Grade 4 toxicity occurs, in which case delay to allow for healing is permitted.

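### Feasibility is a primary endpoint, but the only analysis-set rule keeps patients who completed 60 Gy and attended day 30, which tilts several feasibility measures towards 'feasible'

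*Combined protocol and SAP*

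**What the plan says.** Section 8.1 names feasibility as a further primary endpoint, covering accrual, patients' compliance and whether data collection is practicable. One listed measure is: "Percentage of patients compliant with therapy, defined as receiving at least 60Gy to the head and neck while using prophylactic Dermaprazole as directed". No threshold is attached to it.

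The verdict rests on four criteria, all of which must hold:

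- on toxicity, "No more than 5 patients fail to complete the treatment regimen due to study drug toxicity";
- on cream use, at most 15 patients may fall short of 80% application;
- on accrual, "Enrollment takes no longer than 24 months";
- questionnaire proportions no worse than 80%, 80% and 60% at baseline, on treatment and off treatment.

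Neither count has a denominator.

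Section 8.4, headed Reporting and Exclusions, is the only rule on who is analysed: "All patients enrolled in this study who complete at least 60Gy of radiation and follow up at 30 days post treatment will be included". Section 8.2 continues enrolment "until 30 patients in arm 1 and 15 patients in arm 2 have completed the course of head and neck radiation as evaluable patients". Section 8.3 refers to all enrolled subjects only for descriptive demographic and clinical data. Section 10.4 adds: "Adverse events directly related to Dermaprazole may prompt withdrawal from the study". It also says that radiation normally continues.

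**The concern.** Feasibility asks what happens to patients who start the regimen. The 8.4 set consists of patients who got through radiation and came back a month later, so it is selected on part of the outcome being measured. A patient who stops short of 60 Gy, or leaves before day 30, is the kind of patient a feasibility estimate needs. Under 8.4 that patient is not analysed, and under 8.2 a patient who does not complete radiation is replaced.

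For the measures affected, the bias runs one way, towards a favourable result. The cream has not been tested in humans (section 10.3), so early withdrawal cannot be presumed negligible. Because neither count limit has a denominator, two analysts could reach opposite feasibility verdicts from the same data.

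**Working it through.** The plan states no expected feasibility percentage, so there is no figure to reproduce. Its sample size (about 39 calculated, 45 to enrol) is not at issue here.

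**Inputs from the plan.** 30 evaluable Dermaprazole patients (8.2); limits of 5 and 15 (8.1); 60 Gy and day-30 conditions (8.4). Rates of drop-out, toxicity stopping and cream non-compliance are not given; those below are assumptions.

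**1. The 60 Gy component.** In the 8.4 set it is 30/30 = 100%, whatever the true completion rate. If m further Dermaprazole patients start but do not complete, the all-starter figure is 30/(30 + m):

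| m (assumed) | 30/(30 + m) |
|---|---|
| 3 | 30/33 = 90.9% |
| 5 | 30/35 = 85.7% |
| 8 | 30/38 = 78.9% |
| 10 | 30/40 = 75.0% |

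**2. Limit of 5 toxicity failures.** Let q be the true toxicity-stop rate and s the share of those patients who fall outside the 8.4 set and are replaced.

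- Rate within the set: q(1 − s)/(1 − qs)
- Starters needed for 30 in the set: N = 30/(1 − qs), rounded up
- Pass probability in the set: P(Binomial(30, rate in set) ≤ 5)
- Pass probability over all starters: P(Binomial(N, q) ≤ 5)

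With q = 20% (assumed):

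| s | Rate in set | Pass, set of 30 | N | Pass, all starters, limit 5 |
|---|---|---|---|---|
| 0 | 0.200 | 0.43 | 30 | 0.43 |
| 0.5 | 0.10/0.90 = 0.111 | 0.89 | 34 | 0.30 |
| 1 | 0 | 1.00 | 38 | 0.20 |

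At s = 0.5, q = 15% gives 0.97 in the set against 0.63 over 33 starters, and q = 25% gives 0.75 against 0.10 over 35.

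Part of the gap arises because a fixed limit of 5 is stricter over more patients. Read as a proportion, the limit is 5/30 = 16.7%. That is 34/6 = 5.7, still 5 whole patients, at N = 34, so 0.30 is unchanged. At N = 38 it is 38/6 = 6.3, so 6 are allowed, and P(Binomial(38, 0.20) ≤ 6) = 0.34 instead of 0.20.

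**3. Limit of 15 below 80% cream use.** Assume 40% non-compliance among patients in the set, a fraction d excluded, and excluded patients counted as failures. The all-starter failure rate is d + (1 − d) × 0.40, and N = 30/(1 − d), rounded up. In the set, P(Binomial(30, 0.40) ≤ 15) = 0.903.

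| d | N | Failure rate | Pass, limit 15 | Pass, limit 50% of N |
|---|---|---|---|---|
| 5% | 32 | 0.43 | 0.734 | 0.836 (16) |
| 10% | 34 | 0.46 | 0.483 | 0.740 (17) |
| 20% | 38 | 0.52 | 0.083 | 0.466 (19) |

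A count shows the reversal: 12 non-compliers in the set plus 5 excluded non-compliers is read as 12 (pass) under 8.4 but 12 + 5 = 17 (fail) over all starters.

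**4. Questionnaires.** Attending day 30 is itself an off-treatment visit, so selecting on it raises the off-treatment return rate. The documents give no return rates, so I attach no figure.

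**5. Enrolment time.** The 24-month criterion is not affected by 8.4.

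**The case against.** The strongest reply is that 8.4 does not say 'only' and does not name feasibility. Some feasibility items, such as reasons for non-enrolment, cannot be computed in the 8.4 set at all, and a count of patients failing to complete the regimen naturally includes non-completers. This shows that the text is ambiguous. It does not supply a denominator, and exclusion remains the natural reading of 8.4's heading.

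Three further points stand and limit the finding.

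- The 60 Gy percentage is not one of the four pass/fail criteria, and its 'as directed' half can still fail among completers. A reader might infer that the compliance measure is wholly circular and by itself makes the study look feasible; the documents do not support that.
- A patient who stops the cream but reaches 60 Gy and attends day 30 is still counted, and 10.4 makes that the usual course. A reader might infer that the toxicity limit passes whatever the reaction rate. That requires every toxicity stop to leave the set, which the documents do not say.
- Replacement lengthens accrual, which the 24-month criterion penalises, and the serious-event stopping rule in 8.1 operates separately. Both are partial safeguards, though neither counts a non-serious reaction that leads to withdrawal.

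**Conclusion.** The concern holds in limited form. Followed as written, 8.4 makes the 60 Gy component of compliance 100% by construction and removes early leavers from the two count limits and the questionnaire proportions, biasing these towards 'feasible'. The size depends on how many patients leave before day 30. If none do, there is no bias; if half of an assumed 20% toxicity-stop group do, the chance of meeting the limit of 5 is 0.89 where an all-starter count gives 0.30. These figures rest on assumed rates, on independent binomial outcomes, and on the set being filled to 30. The 45 in section 8.2 is itself the evaluable target, so the difference between 39 and 45 should not be read as an attrition rate. The point concerns feasibility denominators only. Because the endpoint is primary and the correction is small, it should be made.

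**What to change.** In 8.1, state that:

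- the compliance percentage and the two cream limits are computed over all randomised Dermaprazole patients who were dispensed product, regardless of dose received, withdrawal or 30-day attendance;
- the questionnaire proportions use forms due under the study calendar in both arms, on the same basis;
- a patient withdrawn for study-drug toxicity counts as a failure even if replaced under 8.2;
- the limits of 5 and 15 are either absolute or proportions of the 30 planned (5/30 = 16.7% and 15/30 = 50%).

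In 8.4, state that the 60 Gy and 30-day conditions do not apply to feasibility.

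This takes a few sentences and needs no extra patients or visits. Weekly compliance is already assessed (5.5), and actions taken after adverse events are already documented (10.2); the team should confirm that the reason for each withdrawal is also recorded. The cost is that reported compliance and completion rates will be somewhat lower and the criteria harder to meet, particularly if the limits stay absolute.

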2.1.2 Secondary Objectives

2.2.2.1

To assess the highest grade of CTCAE version 5 radiation dermatitis during radiation treatment

2.2.2.2

To assess the time to occurrence of CTCAE version 5 grade 2 or higher acute radiation dermatitis.

2.2.2.3

To assess the time to healing if CTCAE version 5 grade 2 or higher acute radiation dermatitis develops.

2.2.2.4

To evaluate quality of life via acute and long-term symptoms and symptom scores utilizing the SkinDex16 scoring system.

2.2.2.5

To evaluate the threshold dose at which RD appears in either arm, utilizing skin dose tracking structures (V20 to V80 in 5 Gy increments reaching skin shell contours of "skin minus 3 millimeters" and "skin minus 5 millimeters")

2.2.2.6

To evaluate the threshold dose at which RD appears in either arm, using the same metrics as in 2.2.2.5, but with a new simulation scan in the last week of radiotherapy

2.2.2.7

To evaluate the effect of dermaprazole on inflammatory markers: CRP, TNFa, IL-1b, IL-6, by measuring values before, during, and after treatment. We expect this to give further evidence for the mechanism of action of dermaprazole.

Page 4 of 23

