5.6 Post-Treament Follow-Up

Patients will be followed for up to 60 months after completion of radiation or until death to assess intervention-related tolerance. See study calendar.

- 1. Month 1 visit (30 days after completion of all radiation therapy, +/- 14 days)
- 2. Month 3 visit (90 days after completion of all radiation therapy, +/- 28 days)
- 3. Long Term Follow-Up Visits: Month 6 (M6), Month 9 (M9), Month 12 (M12), Month 18 (M18), Month 24 (M24), Month 36 (M36), Month 48 (M48), and Month 60 (M60) (calculated from completion of all radiation therapy, +/- 28 days)

Assessments include:

- Focused skin exam
- Adverse event/toxicity evaluation, including CTCAE version 5 evaluation of radiation dermatitis with note of components (erythema, epilation, fibrosis, etc)
- SkinDex16 guestionnaire
- Photographic documentation of skin reaction with dermatologist's evaluation of CTCAE version 5 from this photography

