For purposes of this study, an adverse event is considered expected when the events are those related to systems within the radiation treatment field and include: infection, allergy, or short & long-term (greater than 6 month) skin changes.

Radiation: The common side effects of radiation to the head and neck most commonly includes radiation dermatitis (i.e., erythema, blistering, pigmentation changes) and fibrosis/firmness of head and neck in the long-term. Commonly, patients develop dry mouth, changes in taste, pain when swallowing, and weight loss. Long term, some patients can continue to have changes in taste and lymphedema.

Dermaprazole: The interventional cream is not yet tested in humans and reactions *in* vivo (especially in patients experiencing radiation dermatitis) are not yet known. Possible side effects include allergy or infection. Given the success in pre-clinical studies, it is unlikely that the interventional cream would lead to worsened rates of radiation dermatitis and skin integrity, though this is a possibility.

Acute and late designations will be defined by the timing of occurrence from treatment.

- Acute toxicity will be defined as events occurring during or within 90 days of treatment completion.
- Late toxicity will be defined as events occurring or persisting ≥90 days from treatment completion.

Attribution: An attribution scale which will be utilized to attribute relatedness of the adverse event to the radiation treatment or to the Dermaprazole/Aquaphor as determined by the treating investigator or Principal Investigator. Assignment of attribution is the responsibility of the treating investigator or Principal Investigator.

Page 19 of 23

- Definite The AE is clearly related to the study treatment.
- Probable The AE is likely related to the study treatment.
- Possible The AE may be related to the study treatment.
- Unlikely The AE is doubtfully related to the study treatment.
- Unrelated The AE is clearly NOT related to the study treatment.

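### The only stated analysis time is the last patient's Month 3 visit, so long-term SkinDex16 and late toxicity have no analysis at adequate follow-up; the Month 18 visit also needs reconciling

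*Combined protocol and SAP*

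**What the plan says.** Section 8.1 gives the timing: "All endpoints will be evaluated when the last patient completes their 3 Month follow-up visit". The sentence goes on: "although patients will continue with additional regular follow-up visits as described in the protocol schedule". The reason given is that by then "the data would provide accurate estimate of compliance and acute toxicity". Sections 8.3 and 8.4 add no other analysis time. Section 8.3 defines acute toxicity and does not mention late toxicity. Section 8.4 admits a patient to the analysis on 60 Gy and a 30-day follow-up visit, with nothing required later.

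Other sections set longer-term aims:

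- Secondary objective 2.2.2.4: "To evaluate quality of life via acute and long-term symptoms and symptom scores utilizing the SkinDex16 scoring system".
- Section 5.6: "Patients will be followed for up to 60 months after completion of radiation or until death to assess intervention-related tolerance".
- Section 6.2: "Subsequent evaluation at two, three, four and five years will be completed to assess for long-term adverse events/toxicities".
- Section 10.3 defines late toxicity as "events occurring or persisting ≥90 days from treatment completion".
- The calendar in 6.1 schedules skin examination, photography, two CTCAE gradings and SkinDex16 at every late visit.

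The late visit lists differ. Section 5.6 includes "Month 12 (M12), Month 18 (M18), Month 24 (M24" and the later years. The calendar goes from Month 12 to Month 24, and the prose of 6.2 goes from twelve months to two years.

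**The concern.** The timing rule covers every endpoint, but its justification covers only the acute ones. A Month 3 cut suits grade 2 or higher dermatitis, acute toxicity, compliance and the inflammatory markers, because each patient's data on these are complete by then. It does not suit an objective about long-term symptoms, or a toxicity category that begins at about the time of the Month 3 visit. At that cut, the patient enrolled last has essentially no late follow-up, while the patient enrolled first may have more than a year.

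Two things are at stake. First, a long-term SkinDex16 or late-toxicity result reported at the cut would rest on a shrinking group of early enrollees. Second, if the long-term analysis is instead left for later, its timepoint is not fixed in advance and could be chosen after the data have been seen. Late skin effects are of real interest here, since section 10.3 says the cream has not yet been tested in humans.

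The Month 18 mismatch is a separate matter of schedule. It determines which visits exist to be analysed, but it adds no weight to the timing point.

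**Working it through.** **The plan's own figure.** The plan computes nothing on this point. Its only calculated figure is the total of about 39 in section 8.2. With 65% against 20%, two-sided alpha 0.05, 80% power, 2:1 allocation and pooled variance, the pooled rate is (0.65 + 2 × 0.20)/3 = 0.35. The control arm is then [1.96 × √(0.35 × 0.65 × 1.5) + 0.842 × √(0.65 × 0.35 + 0.20 × 0.80/2)]² / 0.45² ≈ 12.8, rounded up to 13. The total is 13 + 26 = 39, which matches. Nothing below depends on it.

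**Inputs.** Accrual T is 12 months expected and 24 at most (8.2). The cut is the last patient's Month 3 visit (8.1). Enrolment is 45, as 30 Dermaprazole and 15 Aquaphor (8.2). Late visits are those in the calendar (6.1), plus Month 18 from 5.6.

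**Assumptions not in the documents.** Uniform accrual, equal time from enrolment to end of radiation, no death or dropout, visits on their nominal dates.

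**Formula.** At the cut, time since end of radiation runs evenly from 3 to T + 3 months. The share with Month m data is max(0, (T − (m − 3))/T).

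| Visit | T = 12 | T = 24 |
|---|---|---|
| M6 | 9/12 = 75% | 21/24 = 87.5% |
| M9 | 6/12 = 50% | 18/24 = 75% |
| M12 | 3/12 = 25% | 15/24 = 62.5% |
| M18 (5.6 only) | 0% | 9/24 = 37.5% |
| M24 | 0% | 3/24 = 12.5% |
| M36, M48, M60 | 0% | 0% |

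**In patients.** At Month 12 this is 45 × 0.25 ≈ 11 to 45 × 0.625 ≈ 28. In the Aquaphor arm it is 15 × 0.25 ≈ 4 to 15 × 0.625 ≈ 9. At Month 24 it is 0 to 45 × 0.125 ≈ 6 patients in both arms together.

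**Overall.** The calendar has seven late visits, so at most 45 × 7 = 315 late patient-visits.

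- T = 12: 45 × (0.75 + 0.50 + 0.25) = 67.5, or 21%.
- T = 24: 45 × (0.875 + 0.75 + 0.625 + 0.125) ≈ 106.9, or 34%.

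Mean follow-up at the cut is 3 + T/2 = 9 to 15 months, and the longest is T + 3 = 15 to 27 months. The 28-day visit windows do not bring Month 36 within reach.

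**Month 18.** Section 5.6 lists eight late visits: 6, 9, 12, 18, 24, 36, 48 and 60. The calendar and 6.2 each give seven, without 18. Because 6.2 is prose, the omission cannot be put down to a badly extracted table.

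**The case against.** The strongest reply is that context narrows the sentence. Section 8.1 names only grade 2 or higher dermatitis and feasibility as endpoints, the rule follows directly on the feasibility measures, and its reason concerns compliance and acute toxicity. It may therefore be meant only for those endpoints. That is a fair guess at intent, but the wording says all endpoints, and even on the narrow reading no time is set for the long-term objective.

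A reader might go further and infer that endpoints are evaluated once only, that long-term data are never analysed, or that five years of visits have no planned use. The documents do not support this. Section 8.1 does not rule out a later analysis. Early enrollees' data from Month 6 onwards would be available at the cut. Sections 5.6 and 6.2 state what the late visits are for. Section 10.5 requires recording of skin changes lasting beyond six months, follow-up of ongoing related events, and annual reports to the monitoring board. Those reports are safety oversight, however, and do not amount to an analysis of an objective by arm.

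It is also true that section 8.3 makes everything outside the primary endpoint exploratory, and that this is a 45-patient pilot. Block randomisation should keep follow-up length similar between arms, so the weakness is thin and incomplete data rather than an expected bias between arms. These points limit how serious the gap is but do not close it.

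**Conclusion.** The concern holds as a gap in specification. The plan states one analysis time, suited to acute endpoints, and none for long-term SkinDex16 or late toxicity. Applied as written, it would use about 21% to 34% of the scheduled late patient-visits, falling from 75% to 87.5% of patients at Month 6 to none at Months 36 to 60. These shares rest on the assumptions stated above. Deaths and dropout would lower the patient counts, and uneven accrual would move the shares in either direction. No accrual period the plan allows brings Month 36 or later data into the stated evaluation.

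The Month 18 contradiction is real, and the three sections must be reconciled. The acute primary endpoint and the sample size are unaffected, so this should be corrected but does not threaten the main result.

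**What to change.** 1. In 8.1, limit the Month 3 evaluation to the acute and feasibility endpoints: grade 2 or higher dermatitis, acute toxicity, inflammatory markers and compliance.
2. In 8.1 or 8.3, state when long-term SkinDex16 and late toxicity will be summarised descriptively by arm, at a fixed follow-up that every patient can reach. One example is after the last patient's Month 12 visit, which falls 12 − 3 = 9 months after the present cut, with a final report at the end of follow-up. The documents do not dictate these dates. What matters is that a date is fixed in advance.
3. Reconcile Month 18 across 5.6, 6.1 and 6.2 so that all three give the same visit list.

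The cost is a few sentences, one schedule correction, and one or two later descriptive analyses, depending on whether both example dates are adopted. No new data collection or change in sample size is needed for the analysis change.
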